### List of Pharmacokinetic Parameters

Abbreviation	Full Expression
AUC	area under the plasma concentration-time curve
AUCinf	area under the plasma concentration-time curve up to infinity
AUCtau	area under the plasma concentration-time curve during dosing interval
AUCtau, ss	area under the plasma concentration-time curve during dosing interval at steady state
Cmax	maximum plasma concentration
Cmax, ss	maximum plasma concentration at steady state
Ctrough	trough plasma concentration
Tmax	time to reach maximum plasma concentration
Tmax, ss	time to reach maximum plasma concentration at steady state

### List of Terms

Term	Definition
AC220	Development code of quizartinib
AC886	Active metabolite of quizartinib

## 1. INTRODUCTION

### 1.1 Background of This Study

Acute myeloid leukemia (AML) is a hematological malignant tumor characterized by autonomous growth of myeloid blast cells (myeloblasts) that are unable to differentiate or further develop into mature white blood cells, and its clinical presentation is diverse. According to “Cancer Registration and Statistics” of the Cancer Information Service, National Cancer Center, the crude prevalence rate of leukemia is 9.6 (11.4 for males and 7.9 for females) per 100 000 people in 2011 and it is increasing each year. The prevalence rate of AML by itself is unknown; however, acute leukemia accounts for about 80% of all leukemias, and AML accounts for approximately 80% of adult acute leukemia cases and 20% of pediatric acute leukemia cases. While AML has become a disease that is considered curable in recent years, the long-term survival rate after complete remission (CR) with chemotherapy in AML patients remains low at about 40%. This is attributable to frequent relapse after remission. How to prevent relapse is a major problem of chemotherapy. To solve this problem, many research studies have identified poor prognostic factors in attempts to stratify AML. In patients with poor prognostic factors, intensified treatment does not necessarily improve the prognosis. Therefore, it is necessary to develop molecular targeting drugs in line with the molecular platform that plays a key role in AML.

FMS-like tyrosine kinase (FLT) 3 mutations, which are found in approximately 30% of AML patients, represent an important poor prognostic factor and are listed as gene abnormalities that can be searched in the World Health Organization (WHO) classification version 4. FLT3 is a Class III receptor tyrosine kinase (RTK), like v-kit Hardy-Zuckerman 4 feline sarcoma viral oncogene homolog (KIT), colony stimulating factor 1 receptor (CSF1R), and platelet-derived growth factor receptor (PDGFR), and contains an intracellular tyrosine kinase domain split in two by the juxtamembrane domain. FLT3 is primarily expressed on hematopoietic progenitor cells and is dimerized and activated by ligand binding, and then involved in hematocyte differentiation and proliferation as well as self-replication of hematopoietic stem cells. FLT3 molecules are expressed on the leukemia cell surface in most cases of AML and acute lymphocytic leukemia, and play a role in the survival and proliferation of leukemia cells. There are two main types of FLT3 mutations: FLT3-internal tandem duplication (FLT3-ITD), which involves repetition of part of the juxtamembrane domain, and kinase domain mutation (KDM), which involves point mutation or deletion of the aspartic acid residue at position 835 (D835) in the tyrosine kinase domain or surrounding residues.

These gene mutations cause FLT3 ligand-independent, constant activation of FLT3 molecules and contribute to the promotion of leukemia cell proliferation via activation of downstream signaling pathways, including signal transducer and activator of transcription 5 (STAT5), mitogen-activated protein kinase (MAPK), and phosphatidylinositol 3-kinase (PI3K)/protein kinase B (AKT). Therefore, mutated FLT3 molecules are recognized as promising target molecules for the treatment of AML.

Quizartinib (Development Code: AC220) is an FLT3 inhibitor developed by Ambit Biosciences Corporation that has higher selectivity and affinity for FLT3 than first generation FLT3 inhibitors (lestaurtinib, tandutinib, midostaurin, sorafenib, sunitinib, etc.). Nonclinical data have demonstrated that quizartinib is a potent and specific inhibitor of FLT3 kinase and several other Class III RTKs (KIT, CSF1R/FMS, RET, and PDGFR $\alpha/\beta$ ) and that it has antitumor activity against FLT3-ITD positive human leukemia cells. Overseas Phase 2 studies have also demonstrated high efficacy of quizartinib in relapsed or refractory AML patients. It is therefore expected that quizartinib will become a new treatment option not only for patients with relapsed or refractory AML, but also for patients with initially diagnosed AML. Due to its selective FLT3 inhibitory activity, quizartinib is also expected to improve the treatment results in a selected population of FLT3-ITD positive AML patients, who are known to have poor prognosis. Against this background, quizartinib received fast track designation in November 2010 in the US. At present, a global Phase 3 study is ongoing mainly in Europe and the US. In Japan, relapsed or refractory AML patients are treated with monotherapy or combination therapy with cytarabine, mitoxantrone, etoposide, fludarabine, aclarubicin, gemtuzumab ozogamicin, and others. None of these therapies, however, provide an adequate therapeutic effect. No standard treatment has been established for these patients. There are also no molecular targeting drugs that can be used for initially-diagnosed AML patients, in whom a high relapse rate is still a problem. In view of this situation, Daiichi Sankyo decided to participate in the Japanese development of quizartinib for AML patients.

## 1.2 Nonclinical Study Data

### 1.2.1 Pharmacology

In a biochemical binding assay using a panel of 441 kinases, quizartinib and its metabolite, AC886, exhibited the highest binding affinity for FLT3 (dissociation constant: 1.3 nM for quizartinib and 0.54 nM for AC886). The binding affinity for other

Class III RTKs (eg, KIT, CSF1R/FMS, PDGFR $\beta$ , and RET) was within 10-fold lower than that for FLT3, and the binding affinity for 4 additional kinases (FLT1, FLT4, discoidin domain receptor tyrosine kinase [DDR] 1, PDGFR $\alpha$ , and vascular endothelial growth factor receptor [VEGFR] 2) was within 100-fold lower than that for FLT3. On the other hand, quizartinib showed a weak inhibitory activity against 118 different enzymes, receptor channels, and transporters, and the 50% inhibitory concentration ( $IC_{50}$ ) was higher than 1  $\mu$ M.

In human MV4-11 leukemia cell line with FLT3-ITD mutations treated with quizartinib and AC886, these compounds inhibited FLT3-ITD autophosphorylation, as well as FLT3-dependent cell proliferation ( $IC_{50}$ : approximately 0.3 nM for quizartinib and 0.26 nM for AC886). Following 28-day (once daily) repeated oral dosing of quizartinib in mice with flank solid tumors established by subcutaneously implanted MV4-11 cells, quizartinib inhibited tumor growth at 1 mg/kg and induced tumor regression at 3 mg/kg and 10 mg/kg. At 10 mg/kg, tumors did not regrow throughout the entire 32-day follow-up period after quizartinib dosing. Quizartinib administered in combination with chemotherapy (cytarabine and daunorubicin) was also confirmed to have superior antitumor activity and be well tolerated in the above-mentioned mouse model.

In a telemetry study in cynomolgus monkeys, quizartinib dose-dependently prolonged the corrected QT interval (QTc) and transiently increased systemic blood pressure at  $\geq 10$  mg/kg; however, no hemodynamic or ECG changes were seen at 3 mg/kg. In the assessment of potential effects of quizartinib and AC886 on potassium current carried by channel formed from hERG subunits ( $I_{Kr}$ ) channel-coded by hERG using a patch clamp approach in HEK293 cells overexpressing human ether-à-go-go related gene (hERG), quizartinib did not inhibit the  $I_{Kr}$  channel, whereas AC886 inhibited the  $I_{Kr}$  channel concentration-independently (maximal inhibition: 30% to 40%). In the assessment of potential effects of quizartinib and AC886 on sodium current ( $I_{Na}$ ), potassium current carried by the channel formed by KVLQT1 (KCNQ1) subunits and minK (KCNE1) b-subunits ( $I_{Ks}$ ), and long-lasting calcium current ( $I_{Ca-L}$ ), quizartinib inhibited  $I_{Ks}$ , and AC886 inhibited  $I_{Na}$ ,  $I_{Ks}$ , and  $I_{Ca-L}$ . In ex vivo studies using rabbit heart preparations, quizartinib and AC886 caused increases in QTc interval at concentrations of  $> 3$   $\mu$ M. It was thus suggested that the effects of the two compounds on potassium currents ( $I_{Ks}$  +  $I_{Kr}$ ) would play a role in QTc prolongation.

### **1.2.2 Pharmacokinetics and Drug Metabolism**

Plasma exposure of quizartinib was approximately dose proportional in mice, rats, dogs,

and monkeys. In all examined species, quizartinib was converted to the active metabolite, AC886. Bioavailability of quizartinib across species ranged from 16% in monkeys to 40% in dogs. The low bioavailability of quizartinib in monkeys was considered to be related to the high metabolic clearance of quizartinib to the active metabolite AC886. The presence of food was suggested to enhance the fraction of administered quizartinib dose absorbed in rats. In rats given repeated doses, there was evidence of accumulated quizartinib, but no evidence of self-induced metabolism. Quizartinib and AC886 were shown to be highly bound to plasma proteins (> 99% in all species tested), and quizartinib was shown to poorly penetrate the brain in rats. Quizartinib was confirmed to be neither an inhibitor (1A2, 2B6, 2C8, 2C9, 2C19, 2D6, and 3A4) nor an inducer (3A4 and 1A) of major human cytochrome P450 (CYP) isoenzymes. AC886 showed weak inhibitory activity against CYP2C8, but had no inhibitory activity against the other isoenzymes, which suggests that AC886 is unlikely to show inhibitory activity against CYPs at physiologic concentrations. Quizartinib and AC886 are substrates for CYP3A4 and P-glycoprotein, and quizartinib is metabolized by CYP3A4 to AC886. On the other hand, CYP2B6, 2C8, 2C9, 2C19, 2D6, and 1A2 are found to be barely involved in the metabolism of quizartinib.

### **1.2.3 Toxicology**

Quizartinib was tested in single-dose and repeated-dose toxicity studies (28-day and 90-day studies in rats, dogs, and monkeys), genetic toxicity studies (in vitro and in vivo), reproductive and developmental toxicity studies (rat), and in vitro neutral red uptake phototoxicity assay using a murine fibroblast line (3T3).

In repeated-dose toxicity studies, the principal organs affected were the lymphoid and hematopoietic organs in all species tested. In addition, toxicologic effects were observed in the kidneys, liver, and genital organs (ovary, vagina, and testis).

Target-organ toxicity appeared to be quizartinib dose- and time-dependent, and most toxicologic findings were reversible following a 28- or 30-day recovery period; however, slight decreases in red blood cell (RBC) and white blood cell (WBC) parameters, minimal bone marrow hypocellularity, and liver crystal deposition (only in dogs) persisted after the end of the recovery period. In 90-day studies, toxicologic findings were evident in high-dose rats and dogs at 10 mg/kg and 15 mg/kg, respectively, and included decreases in hematology parameters, increased liver enzymes, and histopathological changes in bone marrow and lymphoid organs. In 90-day studies in monkeys, the mortality and toxic signs were reported at 10 mg/kg/day, resulting in a dose

reduction to 6 mg/kg/day during the dosing period; these toxicologic findings observed in monkeys were consistent with those seen in rats and/or dogs. The no adverse effect level (NOAEL) from 90-day repeated oral doses was established at 3 mg/kg/day in rats and monkeys and 5 mg/kg/day in dogs. The Cmax and AUC of quizartinib at the NOAEL were 0.82  $\mu$ g/mL and 12.1  $\mu$ g·h/mL in rats, 0.11  $\mu$ g/mL and 0.727  $\mu$ g·h/mL in monkeys, and 0.42  $\mu$ g/mL and 3.93  $\mu$ g·h/mL in dogs, respectively.

Quizartinib was evaluated for genotoxic potential; quizartinib was positive in bacterial reverse mutation assay, but was not genotoxic in chromosomal aberration assay in human lymphocytes, mammalian cell mutagenicity assay, or micronucleus assay in rats. In the mammalian cell mutagenicity assay, it was evaluated whether the positive result obtained from the bacterial reverse mutation assay could be reproduced or not. In mouse lymphoma L5178Y TK+/− cells incubated with quizartinib, no substantial increases in mutation frequency were observed at doses up to the cytotoxicity limit. Consequently, quizartinib is considered to have a low genotoxic risk.

In embryo-fetal toxicity studies in rats, systemic edema was found in fetuses at the maximum dose of 6 mg/kg/day, in addition to decreased fetal weight and delayed skeletal ossification. The NOAEL for embryo-fetal development was considered to be 2 mg/kg/day.

In the neutral red uptake phototoxicity assay, quizartinib had a photo irritation factor of 3.13 and a mean photo effect of 0.122. These results suggested that the compound would have a “phototoxic potential” according to the guidelines at the time of the assay. However, a review of the assay data in accordance with the guidance on photosafety evaluation of pharmaceuticals issued on 21 May 2014 resulted in the conclusion that quizartinib is not phototoxic.

### **1.3 Clinical Study Data**

#### **1.3.1 Phase 1 Study (Study CP0001)**

Quizartinib was tested in 76 AML patients with treatment cycles of intermittent dosing (14 days on the drug followed by 14 days of rest) at doses of 12 mg/day to 450 mg/day, and 28-day continuous dosing at 200 and 300 mg/day.

Dose-limiting toxicities (DLTs) were pyrexia in 1 of 5 patients on intermittent dosing at 135 mg/day, Grade 3 QTc prolongation in 1 of 17 patients on continuous dosing at 200 mg/day, and Grade 3 QTc prolongation in 3 of 8 patients on continuous dosing at 300 mg/day. The maximum tolerated dose (MTD) was determined to be 200 mg/day continuous dosing.

The overall response rate (CR + partial remission [PR]) was 53% in FLT3-ITD positive patients and 14% in FLT3-ITD negative patients.

In this study, plasma specimens were collected from quizartinib-treated patients and were tested in an ex vivo assay of plasma inhibitory activity of quizartinib on FLT3 phosphorylation. Plasma from the patients suppressed FLT3-ITD and wild-type FLT3 (FLT3-WT) autophosphorylation activity. In cells expressing FLT3-WT, higher doses and longer exposures of quizartinib were necessary to eliminate detectable phosphorylated FLT3 as compared with FLT3-ITD-expressing cells.

Moreover, a subset of 20 AML patients in the study were evaluated for the effect of quizartinib on phosphorylated STAT5 (pSTAT5), using a whole blood-based assay. Quizartinib treatment decreased pSTAT5 levels in 10 of 11 FLT3-ITD positive patients and 7 of 9 FLT3-ITD negative patients. There was an enhanced effect on pSTAT5 inhibition in FLT3-ITD positive patients. These data suggest that quizartinib inhibits pSTAT5 production regardless of FLT3-ITD mutation status in AML patients.

### **1.3.2 Phase 2 Studies (Studies AC220-002 and 2689-CL-2004)**

In Study AC220-002 conducted in 333 patients with relapsed or refractory AML, 12 patients received 28-day continuous dosing at 200 mg/day, which is the MTD determined in Study CP0001, and Grade 3 QTc prolongation was reported at this dose in 42% of patients in Study AC220-002. The study demonstrated that the incidence of QTc prolongation tended to be higher in females than in males. To address this issue, the dose of quizartinib was reduced to 135 mg/day for males and 90 mg/day for females during the course of Study AC220-002. After dose reduction, 1 female patient on continuous dosing at 90 mg/day, concomitantly with a strong CYP3A4 inhibitor, experienced Grade 4 QTc prolongation (torsades de pointes [TdP]).

In Study AC220-002, patients were divided into 2 cohorts according to age and previous treatment status. Specifically, AML patients of  $\geq 60$  years old with relapsed or refractory AML after 1 first-line chemotherapy regimen were enrolled in Cohort 1, while AML patients of  $\geq 18$  years old with relapsed or refractory AML after salvage regimen, or relapsed AML after hematopoietic stem cell transplant (HSCT) were enrolled in Cohort 2. In Cohort 1, the composite CR (CRc = CR + [CR with incomplete hematological recovery; CRi] + [CR with incomplete platelet recovery; CRp]) rate was 52% in a subset of FLT3-ITD positive patients, with a median overall survival of 25.3 weeks. In Cohort 2, the CRc rate was 45% in a subset of FLT3-ITD positive patients, with a median overall survival of 22.9 weeks. In Cohort 2, 35% of FLT3-ITD positive

patients proceeded to HSCT, and almost all (94%) of those proceeding to HSCT achieved CRc or PR with quizartinib treatment, with a 1-year survival rate of 39%.

Study 2689-CL-2004 was conducted in 76 FLT3-ITD positive AML patients, who were assigned to 28-day cycles of 30 or 60 mg/day continuous dosing of quizartinib (for both males and females) to evaluate the efficacy and safety of quizartinib at lower doses than those tested in Study AC220-002. In the study, the incidence of QTc prolongation was much lower than that observed in Study AC220-002, indicating that the risk of QTc prolongation was dose-dependent (Table 1.3-1). The study also demonstrated that the CRc rates were comparable to those observed in Study AC220-002 (Table 1.3-2). In Study 2689-CL-2004 as well, 34% of patients proceeded to HSCT, and the patients who underwent HSCT tended to have a longer survival than those who did not.

Common adverse events (AEs) reported in Studies AC220-002 and 2689-CL-2004 were gastrointestinal disorders (eg, nausea, diarrhea, and vomiting), hematotoxicities (eg, anemia, neutropenia, and thrombocytopenia), febrile neutropenia, fever, fatigue, and QTc prolongation. Although the hematologic toxicities appear to be associated with the underlying disease, AML, data suggest delayed recovery or continued suppression of absolute neutrophil count (ANC) and platelets as a consequence of continued treatment with quizartinib.

Table 1.3-1 Maximum Values of QT Corrected for Heart Rate Using Fridericia's Method (QTcF) and Maximum Changes from Baseline in QTcF in Two Phase 2 Studies

Daily Dose of Quizartinib	Study AC220-002			Study 2689-CL-2004	
	90 mg/day (N = 57) † Female	135 mg/day (N = 67) † Male	200 mg/day (N = 12)	30 mg/day (N = 38)	60 mg/day (N = 36)*
Maximum QTcF (ms)					
> 480, ≤ 500 (Grade 2)	21%	13%	33%	5%	14%
> 500 (Grade 3) † Asymptomatic	21%	15%	42%	5%	3%
Maximum change in QTcF from baseline (ms)					
≤ 30	9%	9%	0%	50%	44%
> 30, ≤ 60	46%	51%	8%	47%	36%
> 60	46%	39%	92%	3%	19%

\* Two patients in the 60 mg/day group were randomized but never treated with quizartinib.

Table 1.3-2 Composite Complete Remission and Partial Response Rates in Two Phase 2 Studies

Daily Dose of Quizartinib	Study AC220-002			Study 2689-CL-2004	
	90 mg/day (N = 57) † Female	135 mg/day (N = 67) † Male	200 mg/day (N = 12)	30 mg/day (N = 38)	60 mg/day (N = 38)
CRc rate	47%	45%	42%	47%	47%
PR rate	25%	28%	50%	13%	24%

### **1.3.3 Phase 1b Study (Study 2689-CL-2005)**

In this study, quizartinib was administered in combination with induction and consolidation chemotherapy in initially diagnosed AML patients and the safety and pharmacokinetics were assessed. During the induction phase, cytarabine (200 mg/m^2/day on Day 1 to Day 7), daunorubicin (60 mg/m^2/day on Day 1 to Day 3), and quizartinib (40 mg/day or 60 mg/day on Day 4 to Day 10 or Day 4 to Day 17) were administered for up to 2 cycles. During the consolidation phase, cytarabine (3.0 g/m^2/12 hours on Day 1, Day 3, and Day 5) and quizartinib (40 mg/day or 60 mg/day on Day 4 to Day 10 or Day 4 to Day 17) were administered for up to 3 cycles. AEs frequently reported in the study were nausea, diarrhea, constipation, hypokalemia, hypomagnesemia, neutropenia, vomiting, fatigue, headache, hypophosphatemia, hypotension, pyrexia, and rash. One patient had a fatal outcome due to cardiac arrest after experiencing serious AEs (SAEs) (mucosal inflammation, pleural effusion, and pericardial effusion); however, the causality between cardiac arrest and quizartinib was ruled out.

### **1.3.4 Pharmacokinetics**

Pharmacokinetic data of quizartinib and its active metabolite AC886 from clinical studies in AML patients and healthy volunteers have been evaluated. After administration of quizartinib, the plasma concentrations of quizartinib and AC886 increased rapidly (Tmax of quizartinib, 2 to 8 hours post quizartinib dosing during the first day of dosing). Quizartinib and AC886 had terminal elimination half-lives of approximately 3 days, resulting in approximately 4-fold accumulation from the first day of dosing for exposure at the steady state after daily dosing. Plasma exposure to both quizartinib and AC886 was generally proportional with the dose in the tested dose range of 30 mg/day to 90 mg/day. Overall, Cmax and AUC showed moderate to high variability. Plasma concentrations of AC886 at the steady state paralleled quizartinib levels with a plasma concentration ratio of AC886 to quizartinib (AC886/quizartinib) of 0.5. AC886 is the only major metabolite of quizartinib in the circulation. Quizartinib was mainly eliminated by non-renal clearance. The presence of concomitant ketoconazole, a strong CYP3A4 inhibitor, increased the observed AUCinf of quizartinib approximately 2-fold. The presence of concomitant fluconazole, a moderate CYP3A4 inhibitor, increased the observed AUCinf of quizartinib approximately 1.2-fold.

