Endpoints	Primary	
Safety:
 
Adverse event (AEs), laboratory data, vital signs, body weight, 12-lead ECG
 
Pharmacokinetics:
 
Pharmacokinetic parameters of quizartinib and its active metabolite AC886 in plasma

	Secondary	
Pharmacodynamics:
 
FMS-like tyrosine kinase (FLT) 3-internal tandem duplication (ITD) status, c-v-kit Hardy-Zuckerman 4 feline sarcoma viral oncogene homolog (KIT) mutation status, phosphorylated FLT3 protein levels in blood, phosphorylated signal transducer and activator of transcription 5 (STAT5) protein levels in blood, phosphorylated c-KIT protein levels in blood, inhibitory activity of plasma quizartinib on phosphorylated FLT3 protein
 
Efficacy:
 
Complete remission (CR), CR with incomplete platelet recovery (CRp), CR with incomplete hematological recovery (CRI), partial remission (PR), no response (NR), composite CR (CRc: CR + CRp + CRI), response rate (CRc + PR)

Primary statistical analyses		
Safety evaluation:
 
For AEs that occur or worsen after the start of study treatment, frequency tables will be prepared by event, causality with the study drug or a coadministered drug (cytarabine or an anthracycline drug), and grade according to the Common Terminology Criteria for Adverse Events (CTCAE). DLTs will be assessed by frequency tables. Concerning laboratory data, vital sign measurements, body weight, and 12-lead ECG findings, frequency tables or shift tables will be prepared for categorical data, and summary statistics will be calculated for quantitative data. For QTcF, summary statistics will be calculated, and frequency tables according to the predefined categories will be prepared.
 
Pharmacokinetic evaluation:
 
Concerning plasma concentrations of quizartinib and its active metabolite AC886, summary statistics will be calculated by

dose level at each time point, and changes in the concentrations will be depicted in figures. Summary statistics of pharmacokinetic parameters will also be calculated.

Pharmacodynamic evaluation:

Frequency tables will be prepared for the FLT3-ITD status and c-KIT mutation status. For phosphorylated FLT3, STAT5, and c-KIT protein levels in blood and the inhibitory activity of plasma quizartinib on phosphorylated FLT3 protein, the measured values will be summarized at each time point.

Efficacy evaluation:

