## 6.7 Pharmacokinetics

After 2 mL of blood is collected from each patient, as specified in “Table 6.7-1 Blood Collection Points for Pharmacokinetic Assessment,” the plasma specimens will immediately be stored in a frozen state at  $-90^{\circ}\text{C}$  to  $-70^{\circ}\text{C}$ . The specimens in a frozen state will be submitted to the agency contracted by the sponsor to collect the specimens. Details including the handling of specimens will be specified in separate procedures. The date and time of blood collection will be recorded in the CRF.

Table 6.7-1 Blood Collection Points for Pharmacokinetic Assessment

Treatment Cycle	Treatment Day	Blood Collection Point (Acceptable Limit)
Remission induction therapy	Day 8 * First day of quizartinib administration	Pre-dose 30 minutes ( $\pm 10$ minutes) post-dose
Cycle 1		1 hour ( $\pm 10$ minutes) post-dose 2 hours ( $\pm 10$ minutes) post-dose 4 hours ( $\pm 10$ minutes) post-dose 6 hours ( $\pm 10$ minutes) post-dose
	Day 9	Pre-dose
	Day 15	Pre-dose 2 hours ( $\pm 10$ minutes) post-dose 4 hours ( $\pm 10$ minutes) post-dose

	Day 21 * Last day of quizartinib administration	Pre-dose 30 minutes ( $\pm$ 10 minutes) post-dose 1 hour ( $\pm$ 10 minutes) post-dose 2 hours ( $\pm$ 10 minutes) post-dose 4 hours ( $\pm$ 10 minutes) post-dose 6 hours ( $\pm$ 10 minutes) post-dose
	Day 22	On the specified day
	Day 28	On the specified day
Consolidation therapy Cycle 1	Day 6 * First day of quizartinib administration	Pre-dose 2 hours ( $\pm$ 10 minutes) post-dose 4 hours ( $\pm$ 10 minutes) post-dose
	Day 7	Pre-dose
	Day 13	Pre-dose 2 hours ( $\pm$ 10 minutes) post-dose 4 hours ( $\pm$ 10 minutes) post-dose
	Day 19 * Last day of quizartinib administration	Pre-dose
	Day 28 (-3 days to the day)	On the specified day

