## **7. PHARMACOKINETIC ENDPOINTS**

The following pharmacokinetic parameters will be calculated by a non-compartment model approach using plasma concentration data of quizartinib and its active metabolite AC886 obtained on Day 8 of Cycle 1 and Day 21 of Cycle 1 during the induction phase.  
Day 8 of Cycle 1 during the induction phase: Cmax, Tmax, AU $\tau$

Day 21 of Cycle 1 during the induction phase: Cmax,ss, Ctrough, Tmax,ss, AU $\tau$ ,ss

The details of the method of calculation of pharmacokinetic parameters are specified in the Statistical Analysis Plan.

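### Minor: Day 8 PK sampling has no draw between 6 h and about 24 h, so a first-dose peak late in the protocol's own 2 to 8 h Tmax range cannot be located

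*Combined protocol and SAP*

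**What the plan says.** - **Expected peak.** Section 1.3.4 gives the first-day quizartinib Tmax as "2 to 8 hours post quizartinib dosing during the first day of dosing". It gives no Tmax for AC886 and none at steady state. The same section reports "terminal elimination half-lives of approximately 3 days, resulting in approximately 4-fold accumulation".
- **Sampling.** The table in Section 6.7 headed "Blood Collection Points for Pharmacokinetic Assessment" (Table 6.7-1) sets six same-day draws on Day 8: pre-dose, 0.5, 1, 2, 4 and 6 h, each post-dose draw within 10 minutes. The next draw is Day 9 pre-dose. Day 21 has the same six times, followed by a Day 22 sample. Footnote d) of the induction schedule, in the Synopsis and again in Table 6-1, lists these times for both days.
- **Use of the data.** Section 7 takes "plasma concentration data of quizartinib and its active metabolite AC886 obtained on Day 8 of Cycle 1 and Day 21 of Cycle 1" and derives parameters non-compartmentally. The list begins "Day 8 of Cycle 1 during the induction phase: Cmax, Tmax" and goes on to AUCtau. Day 21 yields the steady-state counterparts and the trough.
- **Status.** The Synopsis lists "Pharmacokinetic parameters of quizartinib and its active metabolite AC886 in plasma" as a primary endpoint.

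No reason is given for ending the same-day draws at 6 h.

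**The concern.** A non-compartmental Tmax can only be one of the sampled times. The plan expects first-dose peaks as late as 8 h but takes nothing between 6 h and about 24 h. A patient who peaks at 7 or 8 h cannot be told apart from one who peaks at 6 h. Two post-dose draws, at 0.5 and 1 h, precede the earliest stated Tmax of 2 h. What is at stake is the accuracy of Day 8 Tmax in late-peaking patients and, to a much smaller degree, Day 8 Cmax and AUCtau.

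**Working it through.** **1. Grid against range.** The stated range runs from 2 to 8 h, a width of 6 h. The part after the last same-day draw is 8 − 6 = 2 h, one third of that width. A peak there is recorded up to 2 h early.

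**2. Figures that can be checked.** The 2 to 8 h range is an observed result and cannot be re-derived. The half-life can be set against the stated accumulation: 1/(1 − exp(−ke × 24)) with ke = ln 2/72 = 0.00963 per h gives 4.85. A ratio of 4.0 needs a half-life of about 58 h. The two stated values agree only roughly, which does not matter here.

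**3. Model (assumed).** One compartment with first-order absorption:

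- C(t) ∝ exp(−ke·t) − exp(−ka·t), with ka solved from Tmax = ln(ka/ke)/(ka − ke).
- Half-life 72 h from Section 1.3.4. A value of 24 h is my sensitivity assumption for a faster first-day decline.
- AUC over 0 to 24 h by linear trapezoid, compared with the exact curve.

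Worked case, half-life 72 h and true Tmax 8 h: ka = 0.5045 per h.

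- C(6) ∝ 0.9439 − 0.0485 = 0.8954
- C(8) ∝ 0.9259 − 0.0177 = 0.9082
- Ratio 0.8954/0.9082 = 0.986, so Cmax is 1.4% low.

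**4. Planned grid against the grid with 0.5 h replaced by 8 h.**

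| Half-life | True Tmax | Recorded Tmax, planned → swapped | Cmax bias | AUC bias |
|---|---|---|---|---|
| 72 h | 8 h | 6 → 8 h | −1.4% → 0 | −1.9% → −0.8% |
| 24 h | 8 h | 6 → 8 h | −2.5% → 0 | −4.1% → −1.6% |
| 72 h | 7 h | 6 → 8 h | −0.4% → −0.2% | −1.2% → −0.6% |
| 72 h | 4 h | 4 → 4 h | 0 → 0 | −0.2% → −0.5% |
| 72 h | 2 h | 2 → 2 h | 0 → 0 | −0.1% → −0.9% |
| 24 h | 2 h | 2 → 2 h | 0 → 0 | +1.2% → 0.0% |

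**5. How many patients.** The documents give no distribution of Tmax. If a share p peaks after 6 h, the chance of at least one such patient among n is 1 − (1 − p)^n. For p = 10%, 20% and 33% (assumed) this is 47%, 74% and 91% at n = 6, and 72%, 93% and 99% at n = 12, the two ends of the planned sample size.

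**6. Sample count and pairing.** The swapped grid (pre-dose, 1, 2, 4, 6, 8 h) still has six same-day draws. Day 8 ECGs and both sets of phosphoprotein-related samples are taken pre-dose and at 2, 4 and 6 h. The 30-minute draw is paired with none of them, and the 6 h draw stays.

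**The case against.** **The peak is flat, so the gain in Tmax is smaller than a noise-free model suggests.** This stands. At half-life 72 h and true Tmax 8 h, C(6) is 98.6% of the peak. With assumed measurement CVs of 3%, 5% and 10%, the swapped grid records 8 h in only about 63%, 55% and 44% of profiles. With a true Tmax of 6 h it records 8 h in about a third. Averaged over true Tmax values spread evenly from 2 to 8 h, the mean absolute error in Tmax at half-life 72 h goes from 0.69 to 0.52 h without noise, but from 1.35 to 1.50 h at 5% CV and from 2.22 to 2.11 h at 10%. The benefit is the ability to see late peaks, not a uniformly more accurate Tmax.

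**The 30-minute draw is not worthless.** This also stands. At half-life 72 h it is 24% of Cmax when true Tmax is 8 h but 77% when true Tmax is 2 h. Dropping it costs some AUC accuracy in fast absorbers, as the table shows.

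**The benchmark is loose.** Section 1.3.4 draws on both AML patients and healthy volunteers and does not say whether 2 to 8 h spans individuals or study medians. The share of patients affected is therefore unknown.

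**Stronger readings that the documents do not support.**

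- A reader might infer that Tmax is capped at 6 h. It is not: the Day 9 pre-dose sample belongs to the first-dose profile and can be the recorded maximum. It simply cannot locate a 6 to 8 h peak.
- A reader might infer that Japanese Tmax will be set against the overseas range and look falsely short. Section 11.3.4 plans only summary statistics and concentration profiles, with no such comparison, and escalation rests on DLT counts.

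**Conclusion.** The mismatch is real and minor. The grid cannot locate a quizartinib peak in the last 2 h of the range the protocol itself states, for a parameter that is part of a primary endpoint. For a true Tmax of 8 h, the recorded value is 2 h early. The worst losses within the stated range are 1.4% to 2.5% for Cmax and 1.9% to 4.1% for AUC. These are small beside the moderate to high variability that Section 1.3.4 reports for both, with 3 to 6 patients per level.

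The sizes rest on the one-compartment model, the half-lives of 72 and 24 h, and the linear trapezoid. The mismatch itself needs no model. It is shown for quizartinib on the first day only: without a stated Tmax for AC886 or at steady state, the documents cannot show whether 6 h or 8 h is late enough there. Neither the dose decision nor the exposure summary is put at risk.

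**What to change.** On Day 8, replace the 30-minute draw with a draw at 8 h ± 10 minutes and keep the 6 h draw, which is paired with the ECG and biomarker samples. Make the same change on Day 21 so that the first-dose and steady-state grids match. Edit Table 6.7-1 and footnote d) in both copies of the induction schedule (Synopsis and Table 6-1) together. That footnote governs both days, so changing the table alone would create a contradiction.

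The cost is low. The number of samples and the blood volume are unchanged. Dosing is in the morning, and patients are hospitalised throughout the DLT assessment period (Section 5.9). The price is one early-absorption point: for a true Tmax of 2 h at half-life 72 h, AUC bias moves from −0.1% to −0.9%. If that point is wanted, adding 8 h while keeping 30 minutes holds the bias at −0.2%, for one more 2 mL sample per profile.

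If the sponsor prefers the present grid, Section 6.7 should say why 6 h suffices. Either way, the report should give the number of patients whose recorded Tmax falls on the last same-day draw, and should state the expected AC886 Tmax if it is known.
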